1.3 Exploratory Objectives

To describe the prevalence of molecular abnormalities in de-novo AML samples using comprehensive genomic testing.

ENDPOINTS

Primary Endpoints include the event-free survival defined as the time from on study to death, failure to achieve remission or relapse

Secondary Endpoints include

- disease-free survival (DFS) from end of first course of therapy, defined as time from end of first course of therapy to death or relapse
- overall survival defined as time from study entry and from end of first course of therapy
- proportion of patients that are in remission (MRD negative) after course 1 in both the GO and non-GO groups
- Disease-free survival for patients who are MRD negative but lack high or low risk molecular and cytogenetic features, defined as time from end of first course of therapy to death or relapse
- Estimate the proportion of patients that develop cardiac ejection fraction <50% (CTCAE V5.0 grade 2 or greater dysfunction) either during therapy (early cardiotoxicity) or after completion of therapy (late cardiotoxicity)
- Estimate the proportion of patients who develop infection and/or febrile neutropenia during each treatment course
- Estimate the effect of infection and/or febrile neutropenia on duration of hospital admission for each treatment course

Exploratory Endpoints include descriptive analysis of molecular abnormalities in de-novo AML.

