3.4 Aflac Office Monitoring Schedule

The trial will be monitored internally according to the following schedule:

- Study monitoring will occur every 6 months until all subjects have completed intervention;

- Once all subjects have completed intervention, a final monitoring visit will occur within 90 days after the last study related procedures and follow-up are completed for all patients enrolled;
- Additional monitoring may be performed in the event of serious adverse event(s), if deemed necessary by the monitoring committee or if requested by the Principal Investigator.

4.0 **RISK STRATIFICATION**

After completion of first course of chemotherapy (Induction I), patients will be classified into low or high-risk groups.

Low risk

t(8;21)(q21.3;q22) – CBF (*RUNX1-RUNX1T1*)
 inv(16)/t(16;16)(p13.1q22.1) – CBF (*CBFB-MYH11*)
NPM1 positive without associated *FLT3* mutation
Biallelic CEBPA positive
 No High-Risk Prognostic Markers/MRD negative (<0.05%) at end of 1st induction
CBF, CEBPa, NPM positive **and** MRD positive at the end of 1st Induction

High risk

inv(3)(q21q26.3) *MECOM-RPN1* fusion
 t(3;21)(26.2;q22)
 t(3;5)(q25;q34)
 t(6;9)(p23;q34.1)(*DEK-NUP214*)
 t(8;16)(p11.2;p13.3) *KAT6A*(8p11.21) Fusion (for patients who are 90 days or older)
 t(16;21)(p11;q22) *FUS-ERG*
 Inv(16) (p13.3q24.3) *CBFA2T3-GLIS2*
 Monosomy 7
 Monosomy 5/5q-[*EGR1*(5q31) deleted]
KMT2A(*MLL*) (11q23.3)

- t(4;11)(q21;q23)
- t(6;11)(q27;q23)
- t(10;11)(p11.2;q23)
- t(10;11)(p12;q23)
- t(11;19)(q23;p13.3)

 11p15 rearrangement - *NUP98* (11p15.5)
 12p 13.2 rearrangement - *ETV6* – any partner gene
 Deletion 12p to include 12p13.2
FLT3 High Allelic Ratio mutations (AR >0.1)
 10p12.3 rearrangement - *Non-KMT2A MLL T10 Fusions*
 RAM phenotype (high CD56, dim-to-negative expression CD45 & CD38, no HLA-DR)
 MRD positive (>0.05%) at end of 1st induction, excluding those with *CBF, CEBPa, NPM*

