8.4 Data and Safety Monitoring

This study will be centrally reviewed by the Data Safety and Monitoring Board (DSMB) of the Aflac Clinical Research Office.

The DSMB meets quarterly to review all adverse events and deaths and determine whether any patient safety problems necessitate protocol modifications or discontinuation of the trial.

The DSMB will also meet on an *ad hoc* basis if unexpected safety events occur that may necessitate study suspension or closure. The DSMB will discontinue the review of outcomes when this protocol is closed to accrual.

Before each regularly scheduled DSMB meeting, the study coordinator will submit a report including tabular summaries of all reported SAEs, AEs, and deaths on study to date. The report will also include a brief summary of each previously unreported SAE and death, including an assessment of whether the event was unexpected or related to the study.

If the DSMB recommends protocol or informed consent changes during the study, the recommendations will be reviewed by the Protocol Chair and incorporated into the protocol as deemed appropriate. The protocol with incorporated changes will be distributed to the participating PIs after approval by the Emory University IRB.

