- Probable: The adverse event is most likely related to the study drug(s).
- Possible: The adverse event may be related to the study drug(s).
- Unlikely: The adverse event is doubtfully related to the study drug(s).
- Unrelated: The adverse event is clearly not related to the study drug(s).

For an SAE, the Primary Study Coordinator should be notified via phone or email within 24 hours of the study personnel becoming aware of the event, and they will notify the DSMB. A copy of the completed Serious Adverse Event form must also be sent to study coordinator through REDCap within 5 calendar days after the incident. The investigator is responsible for reporting serious adverse events and unanticipated problems (UPs) to the IRB according to the guidelines mandated by the institutional IRB. The PI will report to FDA any serious unexpected adverse reactions (SUSARs) according to FDA regulations. Copies of all serious adverse event reports will be kept on file in the Clinical Research Office of the Cancer Center.

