4. Disease-free-survival MRD negative: Disease-free-survival, defined as time from end of first course of therapy to death or relapse, will be estimated for MRD negative patients who lack high or low risk molecular and cytogenetic features using the Kaplan-Meier method.
5. Cardiac ejection fraction: Descriptive statistics (frequency and percent) will be used to estimate the frequency of patients that develop cardiac ejection fraction <50% (CTCAE V5.0 grade 2 or greater dysfunction) either during therapy (early cardiotoxicity) or after completion of therapy (late cardiotoxicity).

Exploratory Endpoints:

1. Molecular abnormalities: Descriptive statistics will be used to describe the molecular abnormalities seen in de-novo AML samples using comprehensive genomic testing.

Analysis Datasets:

All eligible patients who receive at least one dose of protocol therapy will be included in the primary efficacy analysis. Safety analysis will be conducted using the Safety Population, defined as any participant receiving at least one dose of study treatment.

Interim Analysis:

The rates of infectious and hematologic toxicities with each chemotherapy course are well established from prior COG study AAML0531 (refer to table below). These toxicity rates will be monitored after enrollment of the first 10 patients and subsequently after the next 10 patients are enrolled. While this is highly unlikely to happen, if toxicity rates are exceeding those expected for each course, the study will be stopped.

AAML0531	ADE	ADE +GO	MA	AE	Capizzi
Infection incidence					
Documented infection	35 %	36 %	69%	49 %	67%
Neutropenic fever	31 %	32 %	23%	23 %	18%
Hematologic Recovery (days)					
Median time to platelets >50K	26	28	38	25	42
Median time to ANC >500	30	30	37	27	40

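### Per-course toxicity is compared with AAML0531 only after patients 10 and 20 enroll, and DSMB review of outcomes ends at accrual close with about five patients still on chemotherapy

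*Combined protocol and SAP*

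**What the plan says.** The Interim Analysis paragraph of section 11.1 tabulates AAML0531 figures for each course: documented infection, neutropenic fever, and median times to platelets above 50K and ANC above 500. On timing it says "These toxicity rates will be monitored after enrollment of the first 10 patients and subsequently after the next 10 patients are enrolled". If rates exceed those expected for a course, the study stops. The paragraph gives no data cut for either look and no look after the second. Section 3.0 allows up to 30 patients, and section 11.1 expects about 30.

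Section 8.4 says "The DSMB meets quarterly to review all adverse events and deaths". The board also meets on an ad hoc "basis if unexpected safety events occur that may necessitate study suspension or closure". Before each regular meeting "the study coordinator will submit a report including tabular summaries of all reported SAEs, AEs, and deaths on study to date". The same section then says "The DSMB will discontinue the review of outcomes when this protocol is closed to accrual".

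Other safeguards exist. Under section 8.3.1, for a serious adverse event "the Primary Study Coordinator should be notified via phone or email within 24 hours", and the DSMB is then told. Under section 3.4, "Study monitoring will occur every 6 months until all subjects have completed intervention". The secondary endpoints listed after section 1.3 include "Estimate the proportion of patients who develop infection and/or febrile neutropenia during each treatment course", and the Safety Population in section 11.1 takes in every treated participant.

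**The concern.** The comparison with AAML0531 is the one device in the plan for telling whether a given course is more toxic than expected. Benchmark documented infection runs from 35% to 69% per course, so a listing of events cannot show an excess without a denominator and a comparator. As written, the device does not reach patients 21 to 30 while they are being treated.

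Section 8.4 can also be read as ending DSMB review while some of these children are on myelosuppressive courses and others have courses still to start. Advice on a course that has not begun can still be acted on. Section 2.3 promises close monitoring of infectious and hematologic toxicity, and section 7.2 attributes most of the risk of death and morbidity during therapy to infection. Stopping board review before the last courses fits poorly with both.

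**Working it through.** **Inputs from the plan.** Accrual is 10 to 20 patients a year over two years (section 11.1): 2 × 15 = 30 reproduces the planned enrollment. Induction I lasts 28 days and later courses 28 days or longer (sections 5.1, 5.3, 5.5, 5.7). High-risk patients typically go to transplantation after two or three courses (section 2.1).

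**Assumptions.** Patients arrive at random at a constant rate. Half receive four courses and half receive two; the plan does not give the high-risk share. Each course lasts either 28 days or the longer of its two AAML0531 recovery medians, but at least 28 days: 30 (Induction I), 38 (MA), 28 (AE; its longer median is 27) and 42 (Capizzi). Courses then end on days 30, 68, 96 and 138, or on days 28, 56, 84 and 112.

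**Share outside the interim comparisons.**

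- If each look waits for courses to end, the share for Induction I and MA is (N − 20)/N: 10/30 = 33% at N = 30, 5/25 = 20% at N = 25, and none at N = 20.
- For AE and Capizzi the share is X/(X + Y), with X from Bin(10, 0.5) and Y from Bin(20, 0.5). Its mean is 33%, its 5th to 95th percentiles are 18% to 47%, and it is below one third in 45% of trials.
- If data are instead cut when patient 20 enrolls, the courses ended number 19 − 15c/365.25 at 15 a year, with c the day the course ends. For Induction I, 19 − 15 × 30/365.25 = 17.8, and 1 − 17.8/30 = 41%. The same formula gives 44–46% for MA, 48–50% for AE and 52–56% for Capizzi. The plan does not say which cut applies.

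**Patients on chemotherapy at accrual close.** The expected number is 1 (patient 30) plus rate × mean days on chemotherapy/365.25. With recovery medians the mean is (138 + 68)/2 = 103 days.

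- 15 a year: 1 + 15 × 103/365.25 = 5.2
- 10 and 20 a year: 3.8 and 6.6
- 28-day courses (mean 84 days): 3.3, 4.5 and 5.6 at 10, 15 and 20 a year

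**Courses not yet started at accrual close**, 15 a year, recovery medians:

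- MA: 1 + 15 × 30/365.25 = 2.2
- AE: 0.5 × (1 + 15 × 68/365.25) = 1.9
- Capizzi: 0.5 × (1 + 15 × 96/365.25) = 2.5
- Total 6.6; 5.1 and 8.1 at 10 and 20 a year; 4.7 to 7.4 with 28-day courses

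**Time to the last chemotherapy course.** In simulation of 40,000 accruals of 30 patients, the mean from accrual close to the end of the last course is 95 to 119 days at 15 a year and 92 to 122 days across 10 to 20 a year. The simulation also reproduces the counts above. On quarterly dates, 92/91.3 to 122/91.3 is 1.0 to 1.3 meetings.

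**Sensitivity to the high-risk share.** Taking 30% to 60% high-risk, with transplantation after two or three courses, the second term at 15 a year runs from 3.2 to 5.1, so the count with patient 30 is about 4 to 6. The most extreme combination at 20 a year approaches 8.

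**The case against.** Four arguments have weight.

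*All 30 patients are summarized at the end.* This stands. The benchmark table is in the same section, so the full series can be set beside it. A reader might infer that patients 21 to 30 are unmonitored or will never be compared with AAML0531. The documents do not support that: quarterly and ad hoc DSMB meetings, serious-event notification, office monitoring and the final summaries all cover them in part. What is missing is a prespecified comparison while they are on treatment.

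*Section 8.4 ends review of outcomes, not of adverse events.* This stands in part. A reader might infer that all DSMB safety review stops at accrual close. Section 8.4 names adverse events and deaths separately, and section 8.3.1 sets no accrual cutoff on passing serious events to the board. The sentence is ambiguous, and no DSMB meeting after accrual close is described.

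*Two looks are a defensible choice, because stopping mainly protects future enrollees.* This stands against a third formal look. Results on patients 21 to 30 come too late to affect enrollment. The rule also has no margin. Read literally, with any observed documented-infection rate above benchmark counting and true rates equal to benchmark, the chance of a trigger at the first look is already about 96% on ended courses (half the patients reaching AE and Capizzi). A further look under that rule adds almost nothing. The margin is a separate issue.

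*The timing figures look more precise than they are.* This stands. The 138 days is a sum of medians and not an upper limit, since courses may run beyond 28 days. If half of the two-course patients receive a third course, courses not started rise from 6.6 to about 7.5.

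None of this puts per-course rates or recovery times before the DSMB for patients still being treated.

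**Conclusion.** The point holds as one of timing and coverage, and it should be fixed. If 30 enroll, at least about a third of Induction I and MA courses, and on average about a third of AE and Capizzi courses, lie outside any prespecified interim comparison. The share is larger if data are cut at enrollment. The gap shrinks with smaller enrollment and, when looks wait for ended courses, is nil at 20 patients.

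At accrual close roughly 3 to 7 patients are on chemotherapy (about 5 at 15 a year) and about 5 to 8 courses have not started. The last course ends about 3 to 4 months later on average, longer if recovery is slow. These counts rest on the assumed half-and-half split between four and two courses and on the assumed course lengths.

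The gain is oversight of patients still on therapy and a complete per-course comparison. It does not establish that a third stop/go analysis is needed, or that the board certainly stops reviewing adverse events.

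**What to change.** 1. **Section 8.4.** State that DSMB review of adverse events, serious adverse events, deaths and per-course toxicity continues until the last patient completes protocol therapy. For high-risk patients, include protocol transplantation and its early toxicity period. Ending at the last chemotherapy course would miss that period, and the gemtuzumab toxicity table in section 9.4 lists veno-occlusive disease around transplantation.
2. **DSMB report.** Add one table by course to each existing report: courses ended, documented infection, neutropenic fever, and times to platelets above 50K and ANC above 500, beside the section 11.1 benchmarks. Continue it through patients 21 to 30. Infection and febrile neutropenia by course are already needed for the secondary endpoint, and section 8.1 schedules blood counts in each course.
3. **Section 11.1.** State that the looks at 10 and 20 use ended courses, counting a course as ended when it stops for any reason, including death or removal from protocol therapy.

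**Cost.** Wording in two sections, one table, and about one or two more DSMB meetings, somewhat more once transplantation is covered. The looks at 10 and 20 come later. At 15 a year, about 15 × 30/365.25 = 1 patient enrolls during the wait for Induction I, 15 × 68/365.25 = 3 for MA and 15 × 138/365.25 = 6 for Capizzi. The quarterly table covers that wait.

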Given that our rates of treatment associated infection are comparable to published standards along with similar favorable outcomes, we will plan to use our described four cycle cytarabine-intensive regimen piloted in 27 patients as the chemotherapy backbone for this trial. All patients regardless of risk status will receive mitoxantrone-cytarabine as their second course of therapy (Induction II). This will be followed by Intensification I (cytarabine-etoposide) and Intensification II (Capizzi-AraC) for low-risk patients. Patients with high-risk disease will receive an allogeneic HSCT typically after two or three courses of chemotherapy. The third course could be either cytarabine-etoposide or Capizzi-AraC at the treating physician's discretion. High-risk patients unable to receive a HSCT will receive treatment per the Aflac-AML regimen with four cycles of chemotherapy similar to low-risk AML patients.

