5.1 Induction 1 – ADE (10+3+5) with GO

The following therapy guidelines are for patients during Induction I. Patients on Induction I will receive gemtuzumab in addition to ADE therapy based on GO genotyping. Induction I lasts a total of 28 days.

Intrathecal Cytarabine: IT

Given at time of diagnostic lumbar puncture or Day 1.

Age-based dosing:

Age (yrs)	Dose
0-0.99	20 mg
1-1.99	30 mg
2-2.99	50 mg
≥ 3	70 mg

For CNS positive patients: add twice weekly IT AraC doses until CNS is clear, plus two additional treatments. A minimum of four intrathecal treatments are to be administered during the period of three weeks following diagnosis.

Cytarabine: Slow IV Push (e.g., over 1-2 minutes)

100 mg/m²/dose (3.3 mg/kg/dose if BSA < 0.6 m²) every 12 hours (total of 20 doses) on Days 1-10.

Daunorubicin (DAUN): IV over 15 minutes

50 mg/m²/dose (1.67 mg/kg/dose if BSA < 0.6 m²) every other day (total of 3 doses) on Days 1, 3, 5.

See Section 6 if direct bilirubin is > 2.

Etoposide (ETOP): IV over 60 – 120 minutes

100 mg/m²/dose (3.3 mg/kg/dose if BSA < 0.6 m²) daily (total of 5 doses) on Days 1-5.

See Section 6 if direct bilirubin is > 2.

Gemtuzumab Ozogamicin (GO): IV over 2 hours

3 mg/m²/dose (0.1 mg/kg/dose if BSA < 0.6 m²) once (total of 1 dose) on Day 6 through 10.

GO to be given once when GO genotyping demonstrates CC genotype. It can be given on any day between days 6-10 of Induction 1.

Pre-medicate with an antihistamine such as diphenhydramine, 1 mg/kg IV (max 50 mg), acetaminophen 10-15 mg/kg PO (max 650 mg) and methylprednisolone (1mg/kg) PO/IV. Repeat every 4 hours as needed to prevent post infusion complications.

Following Induction I, the next course (Induction II) starts on Day 29 or when blood count parameters and clinical condition are acceptable (whichever occurs later). This should not precede the end of course marrow exam.

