10.1 CRITERIA FOR REMOVAL FROM PROTOCOL THERAPY AND OFF STUDY CRITERIA

10.2 Criteria for Removal from Protocol Therapy

1. Failure to attain or maintain remission following Induction II ($\geq 5\%$ malignant blasts or extramedullary disease).
2. Relapse after Induction II of any site following remission.
3. Refractory CNS leukemia following 6 doses of IT cytarabine therapy in Induction I or Induction II.
4. CNS leukemia at start of Induction II after treatment for CNS leukemia in Induction I.
5. Grade 3 or greater neurotoxicity from HD cytarabine or,

6. Other intolerable or unacceptable toxicity secondary to the standard chemotherapy backbone.
7. Refusal of further protocol therapy by patient/parent/guardian.
8. Completion of planned therapy.
9. Physician determines it is in patient's best interest.
10. Development of a second malignancy.
11. Graft failure

Patients who are off protocol therapy are to be followed until they meet the criteria for Off Study (see below). Follow-up data will be required unless consent was withdrawn.

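### The interim rule stops the study on any excess over AAML0531 point values, without a margin, a denominator, a choice of table rows, or a statement whether one course or all must exceed

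*Combined protocol and SAP*

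**What the plan says.** Section 11.1, under Interim Analysis, tabulates AAML0531 results for five course columns (ADE, ADE+GO, MA, AE, Capizzi) and four rows: documented infection, neutropenic fever, median days to platelet recovery and median days to ANC recovery. On timing it says "These toxicity rates will be monitored after enrollment of the first 10 patients and subsequently after the next 10 patients are enrolled". The action is "While this is highly unlikely to happen, if toxicity rates are exceeding those expected for each course, the study will be stopped".

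Under Analysis Datasets the same section says "Safety analysis will be conducted using the Safety Population, defined as any participant receiving at least one dose of study treatment". This defines who is in the safety analysis overall, not who counts in a given course at a given look.

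Two other provisions determine how many patients each course will have. Section 5.1 splits Induction I by genotype ("GO to be given once when GO genotyping demonstrates CC genotype"), and section 2.1.1 sends some patients out of the later courses ("Patients with high-risk disease will receive an allogeneic HSCT typically after two or three courses of chemotherapy").

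Separately, the DSMB meets quarterly to "determine whether any patient safety problems necessitate protocol modifications or discontinuation of the trial" (section 8.4), and the study coordinator is told of each SAE "within 24 hours of the study personnel becoming aware of the event, and they will notify the DSMB" (section 8.3.1).

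**The concern.** The rule is binding, yet it cannot be applied without decisions that the plan leaves open:

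- **Margin.** Any excess over a point value counts, however few patients lie behind it.
- **Any course or all.** The wording allows either.
- **Which rows.** Two of the four rows are median recovery times, which are not rates. The plan does not say whether they, or neutropenic fever, can trigger.
- **Denominator.** Nothing fixes who is evaluable for a course at a look.

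An observed proportion exceeds its own true value about half the time, so a rule without a margin is close to a coin toss for each course. With five courses and two looks, the any-course reading could end a trial whose toxicity is exactly as expected, before the roughly 30 patients for the EFS estimate are enrolled. The all-courses reading has the opposite fault: a serious excess in one course is masked unless the other four also exceed.

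**Working it through.** The plan gives no probability for this rule, so there is no figure to reproduce. The check uses the documented-infection row only.

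**Inputs.** Reference rates p are from the section 11.1 table. Evaluable numbers per course are not in the documents and are assumed here. They reflect an even genotype split and attrition to transplant.

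| | ADE | ADE+GO | MA | AE | Capizzi |
|---|---|---|---|---|---|
| Reference p | 0.35 | 0.36 | 0.69 | 0.49 | 0.67 |
| Assumed n, look 1 | 5 | 5 | 8 | 5 | 3 |
| Assumed n, look 2 | 10 | 10 | 18 | 12 | 10 |
| Smallest count above p, look 1 / look 2 | 2 / 4 | 2 / 4 | 6 / 13 | 3 / 6 | 3 / 7 |

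**Step 1: one course, 10 evaluable, true rate equal to p.** P(X ≥ r) with X ~ Bin(10, p) and r = 4, 4, 7, 5, 7 gives 0.486, 0.513, 0.623, 0.598, 0.568.

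**Step 2: each course over both looks.** With thresholds r1 and r2, and Y ~ Bin(n2 − n1, p) for the patients added between looks:

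P(exceed at either look) = 1 − Σ over x < r1 of P(X1 = x) · P(Y ≤ r2 − 1 − x).

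For ADE+GO: 1 − (0.1074 × 0.9402 + 0.3020 × 0.7491) = 0.673.

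| | ADE | ADE+GO | MA | AE | Capizzi |
|---|---|---|---|---|---|
| Look 1 | 0.572 | 0.591 | 0.526 | 0.481 | 0.301 |
| By look 2 | 0.651 | 0.673 | 0.640 | 0.670 | 0.619 |

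**Step 3: any-course reading.** The chance that some course exceeds cannot be below the largest single-course value, so it is at least 0.673 whatever the correlation. Under independence it is 1 − (0.349 × 0.327 × 0.360 × 0.330 × 0.381) = 0.995. A simulation with within-patient correlation 0.9 gives 0.957.

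| True rates relative to AAML0531 | At least | Independent |
|---|---|---|
| Equal | 0.673 | 0.995 |
| 20% lower | 0.506 | 0.924 |
| 40% lower | 0.327 | 0.689 |

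**Step 4: sensitivity to the assumed numbers (equal rates).**

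- GO share 40% or 60% of Induction I: at least 0.670 in both cases.
- Smaller numbers (4/4/6/3/1, then 8/8/14/8/5), so that not everyone enrolled has finished Induction I: at least 0.736. That maximum comes from Capizzi with one patient at look 1; the next largest course, AE, gives 0.692.
- Every patient on ADE and only Induction I data available (10, then 20): 0.486 at look 1 and 0.567 over both looks. If neutropenic fever also counts, this becomes about 0.77 and 0.87.

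**Step 5: all-courses reading, independent courses.** At look 1: 0.572 × 0.591 × 0.526 × 0.481 × 0.301 = 0.026. By look 2, P(all at look 1) + P(all at look 2) − P(both) = 0.026 + 0.041 − 0.007 = 0.060 (0.19 at correlation 0.9). If ADE+GO infection doubles from 36% to 72%: 0.043 + 0.080 − 0.015, about 0.11 (0.26 at correlation 0.9). If MA rises from 69% to 90%: 0.047 + 0.082 − 0.017, about 0.11.

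**The case against.** The strongest reply has four parts.

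1. **The per-course numbers are assumed.** This stands as a limit. The base case needs every enrolled patient to be evaluable for Induction I at each look, although Induction I lasts 28 days and the newest patient may not have finished. Smaller numbers do not lower the bound, but the all-ADE case does. A reader might infer that 67% is a floor for any way the trial could unfold. The documents do not support that, because they give no per-course numbers.

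2. **The phrase is defensible if all courses must exceed.** That is correct at about 6%, assuming independence. A reader might infer that the plan's reassurance is simply false. It is not, because the wording permits this reading. The price is very little ability to detect trouble in a single course.

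3. **True rates may be below AAML0531.** They may, though section 2.1.1 describes local infection rates as comparable to published standards. Even at 40% lower, the any-course stop is at least 33% on the assumed numbers.

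4. **This is an estimation-driven pilot with DSMB oversight.** A reader might infer that patients lack a safety net. They do not: sections 8.4 and 8.3.1 provide quarterly and ad hoc review and prompt SAE notification. Those provisions set no numerical threshold, however, and do not soften the mandatory stop in section 11.1.

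**Conclusion.** The concern holds: the rule is wrong as written, beyond missing detail. The choice of reading, which the plan does not make, moves the chance of a stop by look 2 from about 6% to 99.5% when toxicity exactly matches the reference (documented infection, assumed numbers, independent courses). Without independence, the any-course figure is still at least 67% on those numbers. The claim that a stop is highly unlikely is therefore unsupported on the any-course reading. On the all-courses reading the claim can stand, but the rule is a poor detector. The single-course result of 49-62% with 10 evaluable patients needs no assumption about attrition or genotype split. The two-look figures are conditional on the assumed numbers. The rule should be rewritten before the first look.

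**What to change.** Keep the looks at 10 and 20 enrolled. Replace the final sentence of the rule with one that:

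1. names the table rows that can trigger;
2. assesses each course separately, so that any single course can trigger;
3. counts, for each course, patients who received at least one dose of it and have completed it, died or come off it;
4. triggers only when the count reaches an exact one-sided binomial boundary against the AAML0531 rate for the number evaluable;
5. states the rule's operating characteristics in place of the claim that a stop is highly unlikely.

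Example for documented infection only, p ≤ 0.05:

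| | ADE | ADE+GO | MA | AE | Capizzi |
|---|---|---|---|---|---|
| Boundary, 10 evaluable | 7 | 7 | 10 | 8 | 10 |
| Boundary, 20 evaluable | 12 | 12 | 18 | 14 | 18 |
| Smallest n that can trigger | 3 | 3 | 9 | 5 | 8 |
| False trigger by look 2, assumed numbers | 0.028 | 0.033 | 0.011 | 0.039 | 0.018 |

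With independent courses the overall false trigger by look 2 is 1 − (0.972 × 0.967 × 0.989 × 0.961 × 0.982) = 0.123; at look 1 it is 0.039. Detection by look 2 is 71% for ADE+GO rising from 36% to 72%, 25% for 36% to 54%, and 45% for MA rising from 69% to 90%.

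If neutropenic fever is also to trigger, the false trigger by look 2 is about 29% at 0.05 per row, 15% at 0.025 and 5% at 0.01, so the level must be chosen with this in view. The recovery medians would need their own definition and margin. The sponsor chooses the rows, the level, and whether reaching a boundary stops the study or pauses accrual for DSMB review.

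The cost is one paragraph and a per-course count of evaluable patients at each look. The downsides should be stated in the plan. Moderate increases are mostly missed. Look 1 is weak: a doubling in ADE+GO is flagged 19% of the time, and MA and Capizzi cannot trigger on the assumed numbers. Any row made report-only stops being a binding trigger. DSMB review and SAE reporting remain the main safeguard.
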